## INTRODUCTION

Small-fiber neuropathies (SFN) selectively affect peripheral small-diameter, thinly myelinated (A-delta) and unmyelinated (C) fibers. Among the conditions that typically involve these fibers are diabetes mellitus (the most frequent); systemic or familial amyloidosis; neuropathy associated with chronic alcohol use; Sjögren syndrome; acquired immunodeficiency syndrome; Fabry disease; hereditary sensory neuropathies; among others. This neuropathy may be characterized by sensory symptoms (loss or reduction of perception of cold and/or heat, altered nociceptive sensation [pain]) and may be accompanied by unpleasant symptoms (paresthesias such as tingling, pins and needles, burning) and dysautonomia. These manifestations negatively affect the physical and mental quality of life of millions of people worldwide.[1–4]

The diagnosis of SFN is often challenging and is based on a combination of clinical evaluation, functional tests, and morphometric examinations.[5–6] Skin biopsy with quantification of intraepidermal nerve fibers, evaluation of thermal thresholds with quantitative sensory testing (QST), and in some cases nociceptive evoked potentials are considered reference standard tests for diagnostic confirmation.[6] However, these techniques are time-consuming to analyze, are not available in primary care settings or routine neurology clinics, and require highly specialized equipment and specifically trained staff.

In terms of functional assessment, QST measures thermal, vibratory, and pain thresholds, evaluating the sensory function of A-delta, C, and A-beta fibers. It is a noninvasive technique that assesses the increase in threshold for the stimuli mentioned in the presence of neuropathy. However, it has some limitations: as a psychophysical test, it is subject to bias; abnormal results have no localizing value to differentiate peripheral from central lesions; and it is time-consuming and available only in specialized centers. Reported sensitivity ranges from 60–85%. The German Research Network on Neuropathic Pain developed a standardized QST protocol that includes seven different tests and measures 13 parameters. Normative reference values are available for both sexes, different age groups, and various body regions such as the face, hand, and foot. QST parameters have been shown to be region-specific, age-dependent, and less sensitive in older patients.[7–16]

Another important neurophysiologic test is the sympathetic skin response (SSR), used to evaluate pre- and post-ganglionic sympathetic activity by measuring changes in voltage at the skin surface after electrical stimulation. This test allows a broader evaluation of autonomic involvement in SFN and is routinely performed in patients with suspected dysautonomia, either due to signs/symptoms or the underlying condition.[17–20]

The diagnostic accuracy of clinical examination alone in SFN has been reported as 54.6%, with a sensitivity of 62.6% and a negative predictive value of 53.7%. To facilitate diagnosis in clinical practice—given the subjectivity of symptoms and the often near-normal physical

exam—tools have been developed such as the Utah Early Neuropathy Scale (UENS), which detects subtle sensory abnormalities. This scale has demonstrated 92% sensitivity and 94% inter-rater reliability for early identification of SFN. One study tested seven different clinical neuropathy scales and their ability to detect neuropathy in patients newly diagnosed with impaired glucose tolerance and found that all tests could distinguish patients with neuropathy from controls with high diagnostic performance. The Modified Toronto Clinical Neuropathy Score (mTCNS) achieved the best diagnostic performance, with 98% sensitivity and 97% specificity. UENS achieved 85% sensitivity and 97% specificity.[5; 21–25]

Nevertheless, given the advantages and limitations of the tests mentioned above, there is a need for tools that can help physicians select/identify patients who require second-level diagnostic testing. The Water-Immersion Wrinkle Test (WIWT) has been used as an indicator of acral sympathetic dysfunction for over 80 years; it is a simple bedside semiologic test that contributes to the noninvasive diagnosis of distal SFN, particularly with autonomic involvement. In the sympathetic cutaneous terminals of distal finger pads, water penetrates through the sweat pores, generating electrolyte changes that induce discharges. These trigger vasoconstriction of the glomus bodies (arteriovenous structures attached to the dermis), reducing their volume and generating wrinkles due to dermal retraction. Elevated water temperature accelerates the process; a 1997 study evaluated wrinkle generation at different temperatures and observed that at low temperatures (20 °C) the time required for wrinkles to appear is approximately 10 minutes and at higher temperatures (45 °C) they appear at approximately 3 minutes.[26] Currently, the standardized technique requires 30 minutes with water at 40 °C. Normally, three or more digital wrinkles are expected according to the wrinkle grading scale. In patients with sensory neuropathy and reduced intraepidermal nerve fiber density, sensitivity of 71% (58%–82%) and specificity of 72% (56%–85%) have been observed. Several studies have reported sensitivity and specificity in the ranges of 70%–90% and 70%–80%, respectively.[27–33]

## JUSTIFICATION

SFN presents diagnostic challenges due to the complexity of symptoms and the variety of available tests. While advanced tests such as skin biopsy, QST, or SSR are useful to confirm the diagnosis, simpler and more accessible tools such as WIWT offer a valuable contribution to initial screening. A comprehensive approach that combines functional, structural, and clinical tests is essential for the effective diagnosis and management of this condition. We propose to estimate the diagnostic accuracy of the Water-Immersion Wrinkle Test and to compare its sensitivity and specificity with routine tests such as QST and SSR. The SFN diagnosis will combine the clinical suspicion of SFN by neuromuscular neurology specialists and at least one clinical scale indicating small-fiber involvement. We propose to use UENS and mTCNS due to their high sensitivity and specificity.

# OBJECTIVES

## Primary Objective

- To determine the sensitivity and specificity of the WIWT for diagnosing SFN against the composite clinical reference at baseline.

## Secondary Objectives

1. To estimate the ROC area under the curve (AUC) of the continuous WIWT score versus the composite reference at baseline.
2. To estimate positive and negative predictive values for WIWT at the observed SFN prevalence at baseline.
3. To assess inter-rater reliability of WIWT wrinkle scoring using ICC(2,1), with two rating sessions 48 hours to 7 days apart.
4. To assess intra-rater reliability of WIWT wrinkle scoring using ICC(3,1), with a second reading 48 hours to 7 days later.
5. To compare diagnostic performance of WIWT with QST and SSR at baseline, including AUC and sensitivity/specificity.

# MATERIALS AND METHODS

## Study design

This prospective diagnostic-accuracy study will be conducted at Hospital Británico, Buenos Aires, Argentina.

## Population

All patients evaluated by the Neurophysiology Service, Neuromuscular Diseases team, Hospital Británico, between November 1, 2024 and November 1, 2025 inclusive, with diagnostic suspicion of small-fiber neuropathy by a neuromuscular neurology specialist.

## Sample size

Based on epidemiological data on pure SFN primarily from a study conducted in the Netherlands[34] that reported an incidence of 12 cases per 100,000 person-years and a prevalence of 53 cases per 100,000 persons, and using an estimated sensitivity and specificity from the literature (80% and 70%, respectively), the required sample size was calculated.

Therefore, the necessary sample size for this study is approximately 30 subjects. This estimate provides a solid basis for the evaluation of the diagnostic test and allows a precise estimation of sensitivity and specificity in the study population. It should be noted that this calculation does not include specific adjustments for low disease prevalence; however, as a

national referral neuromuscular service, the effective prevalence in our institution may be higher than population estimates and may not require low-prevalence adjustments. Moreover, the prevalence described above may be underestimated and higher in the general population.[39]

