All patients with suspected SFN (clinical suspicion plus abnormality on >1 neuropathy rating scale—UENS and mTCNS) will undergo neurophysiological studies such as: sensory and motor nerve conduction studies; QST; routine SSR. Studies such as nerve conduction, QST, and SSR are part of essential standards of care for patients with suspected SFN. In addition to the above, patients included will be offered WIWT, a bedside semiologic test, at no additional cost.

Each operator and observer will be blinded to every other study. A single investigator with experience will perform WIWT. Operators performing QST and SSR will be blinded to each other and to WIWT. QST and SSR operators have extensive experience in their field.

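### The Sample size section calls about 30 subjects precise for sensitivity and specificity, yet at the plan's own 80% and 70% the wider 95% interval spans about 39 to 47 points even at the best split

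*Combined protocol and SAP*

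**What the plan says.** The primary objective is estimation, with no performance threshold or hypothesis: "To determine the sensitivity and specificity of the WIWT for diagnosing SFN against the composite clinical reference at baseline". The Sample size section cites a Dutch survey's incidence and prevalence and takes 80% sensitivity and 70% specificity from the literature. It concludes that "the necessary sample size for this study is approximately 30 subjects", and adds that this number "allows a precise estimation of sensitivity and specificity in the study population". It also states that "this calculation does not include specific adjustments for low disease prevalence".

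The visible text gives no target width, confidence level, formula or expected number of patients with and without SFN. The Population section describes one cohort, patients "with diagnostic suspicion of small-fiber neuropathy by a neuromuscular neurology specialist", and the statistical sections compare those with and without SFN inside it. Statistical methods defines sensitivity and specificity as proportions and names no interval. Statistical analysis refers to STARD in general terms.

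**The concern.** Sensitivity is estimated only in reference-positive patients and specificity only in reference-negative patients. Thirty subjects are therefore not 30 observations for either primary measure: the two denominators add up to 30, and enlarging one shrinks the other.

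The primary objective has no threshold to test, so precision is what has to justify the sample size. If 30 does not deliver it, a reader may take a point estimate such as 70% specificity as firm when the data are compatible with a very wide range. The Introduction offers a scale for this: "Several studies have reported sensitivity and specificity in the ranges of 70%–90% and 70%–80%, respectively". Those spans are 20 and 10 points.

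**Working it through.** **Inputs.** N = 30, sensitivity 0.80 and specificity 0.70 (Sample size). One cohort (Population). The 95% level is assumed; it matches the two-sided 0.05 in Statistical methods. The splits are assumed, because none is given.

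**Can 30 be reproduced?** Not from the visible inputs, because no target half-width d is stated. With n = 1.96² p(1−p)/d² and d = 0.15:
- sensitivity: 3.84 × 0.16 / 0.0225 = 27.3, so 28 patients with SFN
- specificity: 3.84 × 0.21 / 0.0225 = 35.9, so 36 patients without SFN

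Sensitivity alone lands near 30 at ±15 points, but both measures together need 28 + 36 = 64. This shows only how a figure near 30 could arise; it is not evidence of what was done.

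**Interval widths.** For n1 patients with SFN and 30 − n1 without:
- Wald: width = 2 × 1.96 × √(p(1−p)/n)
- Wilson: width = 2 × 1.96 × √(p(1−p)/n + 1.96²/(4n²)) / (1 + 1.96²/n)
- Exact (Clopper-Pearson): from the 0.025 quantile of Beta(x, n−x+1) to the 0.975 quantile of Beta(x+1, n−x)
- Averaged: the sum over x of the Binomial(n, p) probability times the width at x

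At planning values, x = np, which need not be a whole number.

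**Best split.** The split that makes the wider of the two intervals as narrow as possible is 13/17 under every method below. For Wald:
- sensitivity: 3.92 × √(0.16/13) = 43.5 points
- specificity: 3.92 × √(0.21/17) = 43.6 points

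| Method at 13/17 | Sensitivity | Specificity |
|---|---|---|
| Wilson, averaged | 39.0 | 38.9 |
| Wilson, planning values | 40.6 | 40.0 |
| Wald | 43.5 | 43.6 |
| Exact, averaged | 44.9 | 44.5 |
| Exact, planning values | 46.9 | 45.9 |

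**Other splits**, averaged widths in points (sensitivity, specificity):

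| SFN / non-SFN | Exact | Wilson |
|---|---|---|
| 10/20 | 50.5, 41.3 | 43.3, 36.4 |
| 15/15 | 42.0, 47.1 | 36.8, 40.9 |
| 20/10 | 36.7, 55.9 | 32.6, 47.5 |
| 24/6 | 33.6, 67.7 | 30.1, 56.0 |

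**Bound.** Even if all 30 patients served a single denominator, the Wald widths would be 28.6 points for sensitivity or 32.8 for specificity.

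**Against the Introduction's ranges.** At 13/17 the narrowest specificity interval is 38.9 points, and 38.9/10 = 3.9 times the published span. With 17 reference-negative patients, the exact lower limit exceeds 70% only at 16/17 or 17/17. If true specificity is 80%, that has probability 17 × 0.8¹⁶ × 0.2 + 0.8¹⁷ = 0.096 + 0.023 = 0.12. If true specificity is 70%, the exact upper limit falls below 80% only at 9/17 or fewer, with probability 0.10; for Wilson it is 10/17 or fewer, with probability 0.22.

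Sensitivity differs. With 13 SFN patients, the exact interval excludes 70% only at 13/13, which has probability 0.9¹³ = 0.25 when the truth is 90%. With 27 SFN patients that probability is 0.72, and 90% is excluded with probability 0.74 when the truth is 70%.

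**The case against.** - **A formula may be missing.** The sentence giving 30 begins as a conclusion, but no calculation precedes it in the text as read. The section's citations also jump from 34 to 39, while the reference list between those entries contains statistical works, one on sample size for diagnostic studies. A formula and a margin may have been lost. This stands as a limit on judging the derivation. A reader might infer that population incidence and prevalence were wrongly used to obtain 30; the visible text does not show that. The widths are unaffected, because they depend only on N, the split and the planning values.
- **No width is promised.** This stands. A reader might infer that the plan misses its own margin, or that some round figure such as 40 points is a limit. The documents set neither.
- **Low and high published values could still be told apart.** This stands for sensitivity. A reader might infer from the width alone that 70% could not be separated from 90%. An SFN-heavy split can do it: an observed 14/20 has an exact upper limit of 88.1%. For specificity the separation would be rare.
- **Few reference-negative patients is only a possibility.** This also stands. Definition and operationalization of variables describes suspected patients as having "clinical suspicion plus abnormality on >1 neuropathy rating scale", but the Justification asks for at least one scale and the inclusion criteria require none. The 24/6 row is an illustration, not a forecast.
- **STARD may bring intervals.** A reader might infer that none will be reported. The documents show only that no method or level is specified.

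**Conclusion.** The precision claim is unsupported by the plan's own inputs. At 80% and 70%, the most favourable division of 30 leaves the wider 95% interval at about 39 to 47 points, depending on method. Less balanced divisions leave one measure much worse, such as 56 points for specificity at 20/10 (exact, averaged).

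In practical terms, specificity intervals are about four times the 10-point published span at the best split, so the study could rarely separate 70% from 80% specificity. No equivalent statement is made for sensitivity.

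The conclusion rests on a 95% level and assumed splits, but the best-split result covers every division of 30. It does not show that 30 is an unacceptable size for a single-centre study. It shows that the word precise does not describe what 30 will yield.

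**What to change.** Keep the sample size at about 30.

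1. **Sample size.** Replace the sentence claiming a solid basis and precise estimation with wording such as: With about 30 subjects, sensitivity and specificity will be estimated imprecisely. Assuming 80% and 70%, the expected exact (Clopper-Pearson, averaged over binomial outcomes) 95% confidence interval widths for sensitivity and specificity are about 50 and 41 points with 10 SFN and 20 non-SFN patients, 42 and 47 with 15 and 15, and 37 and 56 with 20 and 10. Specificity will be less precise still if fewer patients are reference-negative (34 and 68 with 24 and 6).
2. **Statistical methods.** State that sensitivity and specificity of the wrinkle test are reported with two-sided 95% confidence intervals by the same method. This supports the first change. If Wilson is preferred, use it in both places; the widths become 43 and 36, 37 and 41, 33 and 47, and 30 and 56.

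The cost is a short rewording in each section and two intervals in the output, with no extra patients, visits or tests. The downside is that the stated precision becomes less favourable.

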## **Selection criteria**

### *Inclusion*

- Age > 18 years.
- Suspicion of small-fiber neuropathy based on history and/or physical examination by a neuromuscular neurology specialist.
- Sensory and motor nerve conduction studies within normal limits.
- Prior QST performed, regardless of result.
- Prior SSR performed, regardless of result.

### *Exclusion*

- Patients under 18 years of age.
- Individuals who do not wish to participate in the study or who decline informed consent.
- Patients with any contraindication to any of the aforementioned studies.
- Neurophysiological studies demonstrating large-fiber involvement.

## **Source of information, data collection, and processing**

Our hospital cares for patients with neuromuscular diseases. All information required for this study will be stored in an electronic database accessible only to the investigators and sub-investigators and may be verified by IRB members when deemed necessary. Demographic data and variables of interest will be obtained from the Hospital Británico electronic medical record. The information obtained will be maintained during the analysis of this work in an anonymized electronic case report form (CRF), where each patient will be coded using the first letter of the last name and first name plus a combination of the first, third, and fifth (if present) digits of the patient's medical record number, plus a sequential letter according to alphabetical order, so that any investigator/author can return to the original medical record if relevant information is needed, while preventing direct identification of the patient.

Selection and inclusion will take place after patients are informed, their questions are answered, and informed consent is obtained.

## **Definition and operationalization of variables**

After signing consent, data will be obtained from the history and physical examination, including sensory testing of all four limbs to detect alterations in perception induced by cotton, pinprick, and vibration (medial malleolus, distal radial bone), as well as joint-position sense testing at the distal metacarpophalangeal joints of the thumbs and the metatarsophalangeal joints of the hallux. The presence and distribution of sensation and negative and positive signs will be recorded through comparative evaluation of affected and

unaffected skin areas to differentiate the quality of altered sensation and define dermatomal, mono/multineuropathic, and polyneuropathic distribution. Pallesthesia will be quantified using a graduated 128-Hz tuning fork. Cutaneous sensory signs will be assessed by asking the patient to keep their eyes closed and to report sensation induced by tactile stimuli and gentle brushing with cotton and a flat-tip brush (dynamic allodynia), punctate cutaneous stimulation with a pin (punctate allodynia), prick with a disposable needle (hyperalgesia), cooling/heating with tubes of cold/hot water (thermal allodynia), and superficial and deep mechanical sensation through digital pressure on the skin and underlying tissue (static allodynia and hyperalgesia). Altered sensation (e.g., spread, increase and/or persistence, electric-shock sensation) in affected areas (soles of the feet, dorsum of the feet, legs, fingertips, palms, forearms) compared with expected sensation in unaffected areas will be classified as allodynia or hyperalgesia depending on the stimulus used. Sensory signs will be graded as +2, +1 (gain of function), 0, -1, -2 (loss of function) to allow comparison with findings from QST, SSR, and WIWT. These sensory parameters, as well as muscle strength (Medical Research Council—MRC—scale) and deep tendon reflexes of all four limbs, will be included as variables. Signs and symptoms of dysautonomia will also be recorded based on history, physical exam, the patient's medical record, and an orthostatic hypotension test measuring blood pressure supine and after 3 minutes standing. In all patients, routine tests such as laboratory studies, neuroimaging, etc., performed to determine the underlying etiology of the neuropathy will also be included as study variables.

All patients with suspected SFN (clinical suspicion plus abnormality on >1 neuropathy rating scale—UENS and mTCNS) will undergo neurophysiological studies such as: sensory and motor nerve conduction studies; QST; routine SSR. Studies such as nerve conduction, QST, and SSR are part of essential standards of care for patients with suspected SFN. In addition to the above, patients included will be offered WIWT, a bedside semiologic test, at no additional cost.

Each operator and observer will be blinded to every other study. A single investigator with experience will perform WIWT. Operators performing QST and SSR will be blinded to each other and to WIWT. QST and SSR operators have extensive experience in their field.

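### The definition of suspected SFN carries a scale condition that conflicts with the entry criteria and, read literally, with the diagnostic rule; if it decides who can enter, specificity cannot be estimated

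*Combined protocol and SAP*

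**What the plan says.** **Entry.** Population takes patients "with diagnostic suspicion of small-fiber neuropathy by a neuromuscular neurology specialist". Inclusion repeats this ("Suspicion of small-fiber neuropathy based on history and/or physical examination by a neuromuscular neurology specialist") and adds normal nerve conduction studies, "Prior QST performed, regardless of result" and "Prior SSR performed, regardless of result". Population, Inclusion and Exclusion do not mention UENS or mTCNS.

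**Diagnosis.** Justification states: "The SFN diagnosis will combine the clinical suspicion of SFN by neuromuscular neurology specialists and at least one clinical scale indicating small-fiber involvement".

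**Definition of a suspected case.** Definition and operationalization of variables states: "All patients with suspected SFN (clinical suspicion plus abnormality on >1 neuropathy rating scale—UENS and mTCNS) will undergo neurophysiological studies". These studies are nerve conduction, QST and SSR. The same section then offers WIWT to the patients who are included.

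**Reference standard.** Statistical analysis describes a combination of neurological assessments with UENS and mTCNS. It does not say how the elements combine, and no scale cut-off is given. The Primary Objective asks for sensitivity and specificity of WIWT against this composite, and Statistical methods compares patients with and without SFN.

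**Timing.** Source of information, data collection, and processing states: "Selection and inclusion will take place after patients are informed, their questions are answered, and informed consent is obtained". The next section begins "After signing consent, data will be obtained from the history and physical examination" and then describes QST and SSR in the future tense, although Inclusion requires them to have been done already.

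**The concern.** Entry on suspicion followed by classification with a scale is a normal diagnostic-accuracy design, so Population, Inclusion and Justification fit together. The definition of a suspected case does not fit. It adds a scale condition that the entry criteria lack and, read literally, it asks for more abnormal scales than the diagnosis does.

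Specificity is half of the primary objective and needs participants who are negative on the reference. The scales that define the reference also appear in the sentence that sends patients to the tests required for inclusion. If that sentence works as a filter, it removes the reference-negative patients before WIWT is done. If it does not, a reader still finds two scale thresholds in the document, and the analysis section does not say which one applies.

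**Working it through.** **Inputs.**
- Sample size about 30 and WIWT sensitivity 80% (Sample size). That section gives no precision, power or SFN share from which 30 could be rebuilt, so the figure is used only as given.
- mTCNS sensitivity 98% and specificity 97%; UENS sensitivity 85% and specificity 97%, or UENS sensitivity 92% in another report (Introduction).
- Assumed: a true SFN share of 50% to 90% among participants.

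**Step 1: which patients can be reference-negative.** All have clinical suspicion. Write each pattern as UENS/mTCNS, with A abnormal and N normal. The table lists the patterns that enter and are reference-negative.

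| Scale condition at entry | Reference: at least one scale | Reference: both scales |
|---|---|---|
| None (Population, Inclusion) | N/N | N/N, N/A, A/N |
| At least one (definition read as ≥1) | none | N/A, A/N |
| Both (definition read literally) | none | none |

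Under the Justification rule, either version of the scale condition empties the negative group if it is applied at entry. This takes abnormality on a scale and a scale indicating small-fiber involvement to mean the same thing.

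**Step 2: consequence if the condition filters entry.** With 30 participants and 80% sensitivity:
- true positives 30 × 0.80 = 24; false negatives 30 − 24 = 6; false positives and true negatives 0;
- specificity 0/0, and AUC undefined for want of a comparison group;
- PPV 24/24 and NPV 0/6, both fixed by construction;
- sensitivity can still be estimated: 24/30, exact 95% CI 61% to 92%.

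**Step 3: no filter, exactly one abnormal scale.** Let a and b be the probabilities that UENS and mTCNS are abnormal. Then P(exactly one) = a + b − 2·P(both), where P(both) lies between max(0, a + b − 1) and min(a, b). No assumption about correlation is needed.
- With SFN, UENS 0.85, mTCNS 0.98: P(both) is 0.83 to 0.85, so P(exactly one) is 0.13 to 0.17.
- With SFN, UENS 0.92: P(both) is 0.90 to 0.92, so 0.06 to 0.10.
- Without SFN, 3% false positives on each scale: P(both) is 0 to 0.03, so 0 to 0.06. (The 97% specificity is also used alongside the 92% sensitivity, which is quoted without one.)

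Expected number of 30:
- smallest (UENS 0.92, share 50%): 15 × 0.06 + 15 × 0 = 0.9;
- largest (UENS 0.85, share 90%): 27 × 0.17 + 3 × 0.06 = 4.77.

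This gives about 1 to 5 of 30.

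**Step 4: effect on the specificity denominator** (UENS 0.85, share 90%).
- At least one scale: P(both normal) is 0 to 0.02 with SFN and 0.94 to 0.97 without. Negatives: 27 × 0 + 3 × 0.94 = 2.8, to 27 × 0.02 + 3 × 0.97 = 3.5.
- Both scales: P(not both abnormal) is 0.15 to 0.17 with SFN and 0.97 to 1 without. Negatives: 27 × 0.15 + 3 × 0.97 = 7.0, to 27 × 0.17 + 3 × 1 = 7.6.

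The denominator about doubles. At a 50% share the same sums give about 14 to 15 against 17 to 18.

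**Step 5: sensitivity to the false-positive rate.** The 3% comes from a comparison with controls. If suspected patients without SFN scored abnormal on each scale at an assumed 30%, P(exactly one) among them could reach 0.60. With UENS 0.85 and a 50% share, the upper value becomes 15 × 0.17 + 15 × 0.60 = 11.6 of 30.

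**The case against.** Four arguments carry weight on the other side.

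1. A reader might infer that the study will certainly have no reference-negative patients. The documents do not support that. The definition says that all such patients are tested, not only such patients. The sections that govern entry carry no scale condition, prior QST and SSR fit tests already done in routine care, and the analysis sections expect patients with and without SFN. A separate judgement after entry, within the neurological assessments, could also create negatives, although none is described. This stands: the filter is an inference.

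2. A reader might infer that the plan states two rival reference rules. It does not. Only Justification gives a diagnostic rule; the other threshold describes who is suspected. This stands, so the reclassification count applies only if someone adopts that threshold as the reference.

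3. The sign may be a slip for ≥1. The plan treats another boundary loosely: Inclusion asks for age above 18, while Exclusion removes only those under 18. This is plausible and would remove the conflict with Justification. It would leave the conflict with Population and Inclusion, and a filter at ≥1 would still leave no negatives under the Justification rule.

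4. The 1 to 5 of 30 might be read as bounds. It is not a bound, because it uses accuracies partly from patients with impaired glucose tolerance compared with controls, and Step 5 shows how far it can move.

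None of this removes the textual conflict. The timing statements do not settle it either, since tests done before entry could have been ordered under the same definition.

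**Conclusion.** The contradiction is certain: the definition of suspected SFN carries a scale condition absent from the entry criteria and, read literally, is stricter than the diagnosis, while the analysis section gives no positivity rule to resolve this.

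The consequence is conditional. If the scale condition decides who has QST and SSR, and so who can be included, there are 0 reference-negatives among about 30 under the Justification rule, whether the threshold is more than one or at least one. That assumes scale abnormality means the same in both places and that no separate judgement after entry forms part of the reference. If it does not act as a filter, specificity can be estimated; about 1 to 5 of 30 patients would change class if the stricter threshold were used as the reference. That count is illustrative and grows if suspected patients without SFN often score abnormal.

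The point needs correcting before analysis because the stated definition, if followed at entry, removes half of the primary objective, and clearing it up takes a small change of text.

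**What to change.** - Reconcile the definition of suspected SFN with Population and Inclusion. State that study entry and WIWT do not depend on UENS or mTCNS results, and that both scales are scored in every enrolled patient.
- State one reference-positive rule in Statistical analysis. It should match Justification, the only diagnostic rule in the documents, unless the sponsor replaces it in both places. Fix it, with the UENS and mTCNS cut-offs, before WIWT results are analysed. A complete rule also says whether the neurological assessments are the entry suspicion, which is constant among participants, or a later judgement.
- Reconcile the Inclusion requirement for prior QST and SSR with the later statement that patients will undergo them, so that it is clear whether they precede entry. Who should have these tests clinically is not a matter for this point.

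**Cost.** Wording only, if Population and Inclusion already govern entry. If scale-normal patients were not being sent for QST and SSR, the sponsor must decide how they become eligible, and the change is then more than wording.
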